1 BACKGROUND

Approximately 20% of the UK population develop infectious intestinal disease each year (1). It is characterized by the sudden onset of diarrhoea, with or without vomiting. Other symptoms may include nausea, fever and abdominal pain. Most cases are due to an enteric virus, such as the rotavirus, but some are caused by bacterial or protozoal infections (2). The illness usually resolves without treatment within days; however, symptoms are unpleasant and can affect the whole family. Severe diarrhoea can quickly cause dehydration, which may be life threatening if not treated quickly.

Although intestinal infections are often managed at home without seeking professional advice, they still pose a significant burden on health service resources and the economy with many patients and parents missing time from work and seeking advice from healthcare professionals in primary or secondary care (1,3,4). For example, approximately 10% of children younger than 5 years present to healthcare services with gastroenteritis each year (5) and in the UK diarrhoeal illness has been reported to account for 16% of clinical presentations to a major paediatric emergency department (6). While there appears to be a lack of recent data on the economic and healthcare burden of intestinal infections, data from mid 1990s suggested that around 1 in 5 people in England suffered from infectious intestinal disease every year, with around 35,000 hospital admissions and 300 deaths annually and an estimated annual cost to the nation of £0.75 billion (4,7). The treatments recommended for acute diarrhoea by The National Institute for Health and Care Excellence (NICE) guidance are fluid management and nutritional management (1,3). However, standard rehydration management does not reduce the duration of diarrhoea (8) and the challenge of treating diarrhoea itself remains. There is a need for novel treatments, which can decrease the duration of illness and reduce attendances to primary care or emergency departments.

One potential treatment alternative is the use of intestinal adsorbents, also called enterosorbents, which are frequently used in some countries for treatment of diarrhoea (9). A meta-analysis of 13 randomised clinical trials found that diosmectite, a natural clay adsorbent, significantly decreased the duration of acute diarrhoea in comparison with placebo (10). However, the authors concluded that the evidence was not sufficient and future research was needed. Another study has provided evidence that Enterosgel®, an over-the-counter adsorbent consisting of organic methyl-silicic acid, could be effective in treatment of gastrointestinal disorders (11), but there is a need for randomised studies to further investigate its efficacy.

To address the need for more evidence on the efficacy of intestinal adsorbents in the treatment of diarrhoea, the objective of this randomised, multi-centre study is to assess the efficacy, tolerability and safety of Enterosgel® in treatment of acute *ENTO2UK Protocol v.1.4 11/06/2018*

diarrhoea in adult patients. Use of effective over-the-counter treatments could help to reduce NHS costs and economic burden of intestinal infections by decreasing patient visits to primary care and hospitals and by reducing absences from work.

2 OBJECTIVES

To investigate the efficacy, tolerability and safety of the intestinal adsorbent, Enterosgel® (Bioline Products s.r.o, Czech Republic), in treating adult patients with acute diarrhoea.

2.1 PRIMARY OBJECTIVE(S)

The primary objective of this study is to investigate the efficacy of Enterosgel® in reducing the duration of acute diarrhoea.

2.2 SECONDARY OBJECTIVE(S)

The secondary objectives of this study are:

- 1. To investigate the tolerability and safety of Enterosgel®
- 2. To investigate the impact of Enterosgel® on:
 - a) stool frequency
 - b) duration of other symptoms and signs of intestinal infection (i.e. fever, nausea, vomiting, abdominal pain)
 - c) diarrhoea complications resulting in hospitalisation, Accident & Emergency room attendance, nurse/GP home visit or unscheduled visit to the medical practice

2.3 EXPLORATORY OBJECTIVE(S)

The exploratory objective of this study is to investigate the incidence of Irritable Bowel Syndrome (IBS) -related symptoms and gastrointestinal conditions following an acute diarrhoea episode in the two treatment groups. Our hypothesis is that the use of intestinal adsorbents during an acute diarrhoea episode, could potentially reduce the likelihood that more persistent intestinal problems develop after an acute episode. The data from this study will be used as pilot data to help design larger studies in the future, with the aim of understanding the mechanisms of chronic intestinal conditions such as IBS.

3 STUDY DESIGN AND OUTCOMES

3.1 STUDY DESIGN

This is a 1-week randomised, multi-centre, post-marketing efficacy and safety study of a medical device used within its intended purpose. As in many medical device studies, use of placebo in this trial would be difficult. The exploratory treatment is an orally consumed organosilicon gel-like product, and similar products without any potential impact on the study outcomes and with a demonstrated safety profile would be challenging to develop. As all efficacy and safety data will be recorded in patient diaries, the study outcomes will not be subject to assessor bias. The outcomes have been defined to be as standardised as possible in order to minimise any bias resulting from the participants being unblinded.

Randomisation Control Group N=36 (Standard Treatment) **Patients** N=57 (aged 18-55) with acute 30% missing data/withdrawals diarrhoea **Experimental Group** N=104 (Standard Treatment + N=36 Enterosgel) N=57 DAY 0 DAYS DAYS Visit 1,2,3,4,5 6, 7 Phone Call Phone Call DAY 5

Figure 1. Study design.

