3.2 STUDY OUTCOMES

3.2.1 Primary Outcome

Duration of diarrhoea defined as time (hours) from randomisation to first nonwatery stool (soft or firm)

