3.2.2 Secondary Outcome(s)

 Duration of diarrhoea defined as time (hours) from randomisation to last watery stool

Stop Enterosgel if diarrhoea resolved

- 2. Percentage of patients with diarrhoea resolved on Day 3 (i.e. first soft or firm stool recorded on Day 0-3)
- 3. Stool frequency defined as average number of stools/day from randomisation to first soft or firm stool
- 4. Tolerance and safety of Enterosgel® (assessed via Adverse Event (AE) reporting from start of treatment until end of Day 7)
- Percentage of patients with diarrhoea-related complications resulting in hospitalisation, Accident & Emergency department visit, nurse/GP home visit or unscheduled visit to the medical practice from randomisation until end of Day 7
- 6. Duration (days) of the following from randomisation:
 - a) Nausea
 - b) Vomiting
 - c) High body temperature defined as ≥38°C
 - d) Abdominal pain

Patient diary is the data source for all efficacy outcomes. Any AEs related to taking study treatment(s) should also be recorded in the patient diary. Any diarrhoea-related complications resulting in hospitalisation, Accident & Emergency department visit, nurse/GP home visit or unscheduled visit to the medical practice, should be reported by the patient during follow-up calls and recorded by the nurse in practice medical notes and the eCRF.

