The research nurse or GP will then randomise the patient to the intervention group using a computerised randomisation tool. Patients randomised to the Interventional group will be provided with a sufficient amount of Enterosgel® for 5-7 days of treatment and should take Enterosgel® as instructed in the study-specific instructions which will be provided to them (**Appendix A**). Patients randomised to the Control group will not receive any treatment in addition to the standard of care ORS treatment. The details of prescribed ORS treatment and any dietary recommendations will be recorded in the eCRF.

All patients will be provided with a patient diary (**Appendix C**) to record:

- 1. stool times and consistency
- 2. diarrhoea medication use
- 3. other symptoms (fever, nausea, vomiting etc.)
- 4. any AEs

Patients should fill in the patient diary daily from Day 0 until end of Day 7.

Patients will be asked to take a stool sample on the same day at home in a provided clean container. Patients in the Interventional Group should take the stool sample before taking the first Enterosgel® dose. ORS treatment can be started before taking the stool sample. The sample should be taken to the medical practice by the patient or a family member/friend. It will then be delivered to a local laboratory to test for the presence of rotavirus and diarrhoea causing bacteria (i.e.

Campylobacter, Clostridium difficile, Escherichia coli, Salmonella enterica, Shigella), in order to identify the likely cause of the episode. If there is a reason to suspect norovirus infection (i.e. outbreak), this will also be tested for. Patients who have recently travelled abroad will be additionally tested for *Pseudomonas* and *Vibrio cholerae*. A stool sample will only be collected in baseline and the results will be summarised in baseline characteristics.

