6.1.2 Days 1-7

During the study, the patients will fill the patient diary (**Appendix C**) from Day 0 (after randomisation) until end of Day 7, measure their body temperature twice a day, and take ORS as prescribed and ® according to study-specific instructions provided in **Appendix A**.

Every morning between 8 am to 11am, the research nurse will call the patients to ask about the information recorded in the patient diary and record it in the eCRF. On Day 7, the patients should continue to fill the diary after the call until end of the day. After completing the study, the patients should return the patient diaries to the medical practice. A pre-paid envelope will be provided.

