APPENDIX C: PATIENT DIARIES

Randomised, multi-centre study to assess efficacy, tolerability and safety of Enterosgel® in treatment of acute diarrhoea in adults

PATIENT DIARY (CONTROL GROUP)

Patient Identifier:	Date:	_
DIARRHOEA		

After every bowel movement, please write down the time of the movement below. Please also check one option that best describes the consistency of the stool (by placing a check mark or a cross in the relevant column).

	Time (for example 6.15 am)	Liquid/ Watery/ Loose	Soft	Firm/ Solid
Morning 6 am-12 pm				
Day 12 pm-6 pm				
Evening 5 pm-12 am				
Night 12 am-6 am				

ENT02UK

Patient Diary Control Group v.1.0

09/10/2016

SYMPTOMS					
Please circle experience a		ns you have	experienced today, or "	None" if you di	d not
None	Nausea	Vomiting	Abdominal pain	Other	
lf other, pleas	se describe:				
Body tempe	rature in the	e morning: _	°C Body tempera	ature in the eve	ening:°C
TREATMENT	rs				
Every time af	ter taking yo	our oral rehy	dration treatment, pleas	se write down tl	ne time below.
	nn and des		ou took by placing a cro experienced any side ef		
	Time (for examp	le 6.15 am)	Describe any side effe complications	cts or	
Morning 6 am-12 pm					
Day 12 pm-6 pm					
Evening 6 pm-12 am					
Night 12 am-6 am					
Please list h	ere if you h	nave used ar	ny other medication(s) for your diar	rhoea today:
ENT02UK		Patient	Diary Control Group v.1.0	0	09/10/2016

PATIENT DIARY (ENTEROSGEL® GROUP)

Patient Identifier:	Date:	
DIARRHOEA		

After every bowel movement, please write down the time of the movement below. Please also check one option that best describes the consistency of the stool (by placing a check mark or a cross in the relevant column).

	Time (for example 6.15 am)	Liquid/ Watery/ Loose	Soft	Firm/ Solid
Morning 6 am-12 pm				
Day 12 pm-6 pm				
12 piii-o piii				
Evening 6 pm-12 am				
Night 12 am-6 am				

ENT02UK

Patient Diary Enterosgel® Group v.1.0

09/10/2016

SYMPTOMS					
Please circle experience a		s you have	experienced t	oday, or "No	ne" if you did not
None	Nausea	Vomiting	Abdomi	nal pain	Other
If other, pleas	se describe:				
Body tempe	r ature in the	morning: _	°C Body	/ temperatui	re in the evening:°C
TREATMENT	rs				
Every time af	ter taking dia	arrhoea trea	atment, please	write down t	he time below.
	mn and desc				or check mark in the ts which you think could be
	Time (for example	e 6.15 am)	Enterosgel®	Oral rehydration treatment	Describe any side effects or complications
Morning					

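### Section 3.1 says the outcomes are free of assessor bias because all data are in patient diaries. Nurse-recorded complications, investigator-judged causality and a primary outcome self-classified by unblinded patients contradict this.

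*Protocol*

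**What the plan says.** Protocol section 3.1 gives the reason for running without a placebo and then states: "As all efficacy and safety data will be recorded in patient diaries, the study outcomes will not be subject to assessor bias". The next sentence says that the outcomes were standardised "in order to minimise any bias resulting from the participants being unblinded".

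Other sections describe who observes, judges and records:

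- **Primary outcome (3.2.1):** "time (hours) from randomisation to first nonwatery stool (soft or firm"). In the Appendix C diary the patient ticks the "option that best describes the consistency of the stool (by placing a check mark or a cross in the relevant column"). The three columns are Liquid/Watery/Loose, Soft and Firm/Solid.
- **Data source (3.2.2):** "Patient diary is the data source for all efficacy outcomes". Later in the same paragraph, diarrhoea-related complications "should be reported by the patient during follow-up calls and recorded by the nurse in practice medical notes and the eCRF".
- **Daily calls (6.1.2):** "the research nurse will call the patients to ask about the information recorded in the patient diary and record it in the eCRF".
- **Allocation (section 6, Day 0 procedures):** "The research nurse or GP will then randomise the patient", and Enterosgel patients are given the product.
- **Adverse events (7.2):** the site PI decides whether an event is related to the study or its treatments. For an event during a study visit, only one judged related is recorded as an adverse event.

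**The concern.** The sentence in 3.1 is offered as a design safeguard for an open-label trial, and it has two parts. The premise is that every efficacy and safety item is in the diary. The inference is that data in a diary cannot carry assessor bias. The protocol's own procedures contradict the premise, and the inference does not follow when the person filling in the diary knows the treatment.

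The boundary between loose and soft is a judgement, the diary text gives no further criterion for it, and a single tick on the soft side is the primary event. Day-3 resolution and stool frequency (secondary outcomes 2 and 3) are defined by the same event. If patients who take the gel expect to improve and cross that boundary slightly sooner on paper, the comparison shifts towards Enterosgel without any true effect.

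If the sentence stays, the report could present an open-label, self-judged result as protected from this bias.

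**Working it through.** **Step 1. Who assesses what.**

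| Outcome | Who observes or judges | Who records | Masking described |
|---|---|---|---|
| Primary; secondary 1–3 (stool times and form) | Patient | Patient in diary; nurse transcribes by phone | None; patients are stated to be unblinded |
| Secondary 4 (tolerance and safety) | Patient reports; PI judges relatedness | Diary, then study records | None |
| Secondary 5 (complications leading to healthcare contact) | Patient reports on calls | Nurse, in notes and eCRF | None |
| Secondary 6 (nausea, vomiting, pain, temperature) | Patient; thermometer for temperature | Patient in diary; nurse transcribes | None |

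The premise fails for secondary 5, which is routed through the nurse, and for the causality step of secondary 4. The statement in 3.2.2 that the diary is the source for all efficacy outcomes also conflicts with the routing of complications in the same paragraph. The inference fails for the primary outcome, because the assessor is the unblinded patient.

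**Step 2. The plan's own figure.** Inputs from section 8.1: difference 1 day, SD 1.3 days, 5% significance (two-sided reproduces the figure), 90% power.

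n per group = 2 × SD² × (1.960 + 1.282)² / difference² = 2 × 1.69 × 10.51 / 1 = 35.5, so 36. Allowing for 30% loss, 36/0.70 = 51.4, so 52 per group and 104 in total. The plan's figures reproduce.

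**Step 3. How far a modest reporting shift moves the false-positive rate.** This step is illustrative. The protocol gives neither the stool spacing nor the share of patients who would tick early, so both are assumptions: 3 stools a day (8 h apart), and 25%, 50% or 100% of Enterosgel patients ticking Soft one stool early. True effect zero.

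- Mean shift = share × 8 h = 2, 4 or 8 h, which is 0.083, 0.167 or 0.333 days.
- Standard error = 1.3 × √(2/36) = 0.306 days.
- Non-centrality = shift / 0.306 = 0.27, 0.54 or 1.09.
- Rejection probability from the two-sample t-test with 70 degrees of freedom, critical value 1.994:

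| Share ticking early | Shift | p<0.05, either direction | In favour of Enterosgel | In favour of control |
|---|---|---|---|---|
| 0% | 0 h | 5.0% | 2.5% | 2.5% |
| 25% | 2 h | 5.8% | 4.5% | 1.3% |
| 50% | 4 h | 8.4% | 7.7% | 0.6% |
| 100% | 8 h | 18.9% | 18.8% | 0.1% |

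(Rows may differ by 0.1 through rounding.) With all 52 per arm evaluable, the totals are 6.2%, 9.9% and 25.4%.

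**The case against.** The strongest defence is that the protocol does not hide the open label. The sentence after the claim concedes that participants are unblinded, and *assessor* may have been meant as a third party distinct from the patient. On that reading the claim is narrower, but it is still wrong for complications and for adverse-event causality, where site staff record or judge. A reader of a trial report would also not take the sentence so narrowly.

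The second defence is that transcription is well controlled. The nurse transcribes diary entries and does not classify stools. Diaries are returned (6.1.2), the eCRF must agree with source or the discrepancy be explained (9.1), data are monitored against source (9.2), and data-entry problems that prevent verification of the primary outcome count as a protocol violation (9.3). This stands, so it would be wrong to infer that nothing protects the data. These checks cannot correct the tick itself.

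Several stronger readings are tempting, and the documents do not support them:

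- *GPs assess outcomes.* The GP may randomise, but no section has the GP judging an outcome in that capacity; 7.2 names the PI.
- *Practice staff decide the home and practice visits counted in secondary outcome 5.* The protocol does not say who initiates them.
- *The diary has no place for complications.* It has a free-text column for side effects or complications, tied to treatment. It has no dedicated field for healthcare attendances.
- *Almost all false positives would favour Enterosgel.* At the 2 h shift the share is about 78% (4.5/5.8).
- *Every outcome is equally exposed.* Stool times and thermometer readings leave less room for judgement.

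Secondary outcome 1 (time to last watery stool) is a partial check on a single early soft stool, but the patient classifies it too.

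**Conclusion.** The statement in 3.1 is wrong as written and should be corrected. The contradiction is internal to the protocol and rests on no assumption: complications are recorded by the nurse from calls, causality is judged by the PI, and the primary event is one stool classified by an unblinded patient.

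The size of any resulting bias is unknown. Under the assumptions shown, the chance of a significant result with an inactive device rises from 5% to between 5.8% and 18.9% with 36 per arm. A reader might infer that expectation alone would readily make this a positive trial. The figures do not show that: even if every Enterosgel patient ticked one stool early, about 81% of such trials would stay non-significant, and the 8 h shift is one third of the 1-day target difference.

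That site staff are unblinded is an inference from who randomises, from the product being handed out at the practice, and from the absence of any described masking. The open-label design is not itself the fault; the claim made for it is.

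**What to change.** 1. In 3.1, replace the sentence with a statement that outcomes are assessed by unblinded patients and, for complications and adverse-event causality, by unblinded site staff, so that the result estimates the open-label effect of adding Enterosgel to ORS.
2. In 3.2.2, correct the diary-only source statement so that it excepts secondary outcome 5 and names the calls, medical notes and eCRF as its source.
3. Derive the primary outcome by program from the returned stool pages, with the person running the derivation masked to arm. This removes discretion after the diary is written; it does not remove the patient's own expectation, and the text should say so.
4. In secondary outcome 5, report hospitalisation and A&E attendance separately from home and practice visits.

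Two further changes might suggest themselves. Removing the arm name from the stool page is not worth making: the patient takes the gel and records each dose, so it blinds nobody. A sensitivity rule that accepts the first soft or firm stool only if no watery stool follows within 24 h can supplement secondary outcome 1 where watery stools follow an early Soft tick. It should not be presented as a remedy for expectation bias: if the last watery stool is relabelled Soft, no watery stool follows and the rule changes nothing.

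Cost: protocol wording, one masked derivation and one split table on data already planned. The downside is a less favourable statement on bias and slightly more analysis work.

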3.2 STUDY OUTCOMES

3.2.1 Primary Outcome

Duration of diarrhoea defined as time (hours) from randomisation to first nonwatery stool (soft or firm)

3.2.2 Secondary Outcome(s)

 Duration of diarrhoea defined as time (hours) from randomisation to last watery stool

Stop Enterosgel if diarrhoea resolved

- 2. Percentage of patients with diarrhoea resolved on Day 3 (i.e. first soft or firm stool recorded on Day 0-3)
- 3. Stool frequency defined as average number of stools/day from randomisation to first soft or firm stool
- 4. Tolerance and safety of Enterosgel® (assessed via Adverse Event (AE) reporting from start of treatment until end of Day 7)
- Percentage of patients with diarrhoea-related complications resulting in hospitalisation, Accident & Emergency department visit, nurse/GP home visit or unscheduled visit to the medical practice from randomisation until end of Day 7
- 6. Duration (days) of the following from randomisation:
 - a) Nausea
 - b) Vomiting
 - c) High body temperature defined as ≥38°C
 - d) Abdominal pain

Patient diary is the data source for all efficacy outcomes. Any AEs related to taking study treatment(s) should also be recorded in the patient diary. Any diarrhoea-related complications resulting in hospitalisation, Accident & Emergency department visit, nurse/GP home visit or unscheduled visit to the medical practice, should be reported by the patient during follow-up calls and recorded by the nurse in practice medical notes and the eCRF.

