4.4 WITHDRAWAL CRITERIA

Patients can withdraw consent at any time without providing a reason. No further

data will be collected after a patient withdraws consent or is withdrawn from the study, but data collected before withdrawal can be used.

In case of the following the patient should be withdrawn from the study:

- 1. Refusal to continue the use study treatments
- 2. Significant deterioration of the patient's status
- 3. Serious Adverse Event (SAE)
- 4. Serious adverse reaction
- 5. Changes in diagnosis
- 6. Major protocol violation (affecting patient safety and/or scientific quality of the data)

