8 STATISTICS

8.1 POWER CALCULATION

The power calculation for this study is based on demonstrating superiority of the Interventional Group on the primary outcome, duration (days) of diarrhoea. Power was calculated using an online power calculator for continuous outcome superiority trial (Sealed Envelope Ltd. 2012. Available from: https://www.sealedenvelope.com/power/continuous-superiority/).

In line with some previous studies, we assumed a standard deviation for the duration of diarrhoea of 1.3 days (14,15). In order to detect an average decrease of 1 day in the duration of diarrhoea in the Interventional group compared with the Control group, 36 patients in each group are required for 90% power to demonstrate superiority at 5% significance level. Accounting for a combined patient withdrawal and missing data rate of 30%, 52 patients will need to be randomised into each group. Therefore, the total number of patients enrolled will be 104.

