8.2 STATISTICAL ANALYSES

A CONSORT flow diagram will show the progress through the parallel randomised trial (that is, enrollment, intervention allocation, follow-up, and data analysis). The baseline characteristics of the groups will be summarised as mean (standard deviation) or n (%). The baseline characteristics will not be compared statistically, in line with CONSORT.

Primary analysis will be conducted on an intention-to-treat basis. The primary outcome will be summarised as mean (standard deviation). The Interventional

group and Control group will be compared using a t-test or Mann Whitney test, as appropriate. A generalised linear model will undertaken to control for an potentially confounding variables, e.g. age and gender.

Secondary outcomes will be summarised as mean (standard deviation) or n(%) median (interquartile range). The Interventional group and Control group will be compared using a t-test or Mann Whitney test for continuous data (e.g. duration of nausea, vomiting and fever) and chi-square tests for categorical data (e.g. complication rate).

A p-value of <0.05 will be considered to indicate statistical significance and all analyses will be undertaken on STATA.

A 30% drop out has been taken into account in the sample size calculation for the primary analysis to allow for missing data. The extent and reasons for missing data will be reported and investigated to see whether the data is missing at random. This will inform which methods to handle missing data will be employed. Sensitivity analyses will be performed as appropriate.

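### Secondary outcome 1 ends diarrhoea at the last watery stool without evidence that it was the last, so a patient who leaves while ill can enter the ITT analysis with a short, complete-looking duration

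*Protocol*

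**What the plan says.** Section 3.2.2, item 1, reads "Duration of diarrhoea defined as time (hours) from randomisation to last watery stool". Nothing else in the protocol qualifies the word last.

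Four other provisions determine how that definition works in practice:

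- **Observation.** Section 3.2.2 adds "Patient diary is the data source for all efficacy outcomes", and section 6.1.1 says "Patients should fill in the patient diary daily from Day 0 until end of Day 7".
- **Withdrawal.** Section 4.4 lists reasons for which a patient should be withdrawn, among them "Significant deterioration of the patient's status", a serious adverse event and refusal of study treatment. It states that no further "data will be collected after a patient withdraws consent or is withdrawn from the study, but data collected before withdrawal can be used".
- **Expected loss.** Section 8.1 says "Accounting for a combined patient withdrawal and missing data rate of 30%, 52 patients will need to be randomised into each group".
- **Analysis.** Under section 8.2, secondary outcomes are "compared using a t-test or Mann Whitney test for continuous data". Missing-data methods are to be chosen once the extent and reasons have been examined.

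The primary outcome (section 3.2.1) is built differently. It ends at an observed event, the first soft or firm stool, so a patient who never records one has no value.

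**The concern.** A stool can be known to be the last watery one only if observation continues after it. The definition does not ask for that, so anyone with at least one watery stool after randomisation has a number, however early the diary stops. A patient with a watery stool at 19 hours who is withdrawn for deterioration at 20 hours has a value of 19 hours, the same as a patient who recovered at 19 hours.

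Some of the listed withdrawal reasons are tied to still being ill. The trial is open-label and only one arm takes the device, so unequal loss is plausible. At stake is the ITT comparison on this outcome: loss of sick patients shortens the recorded mean in the arm where it occurs, and neither named test can tell a shortened value from a real one.

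**Working it through.** **The plan's own figure.** With SD 1.3 days, a difference of 1 day, 90% power and 5% two-sided significance (section 8.1; two-sided is assumed because it reproduces the figure):

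n = 2 × (1.960 + 1.282)² × 1.3² / 1² = 35.5, so 36 per group; 36 / 0.70 = 51.4, so 52 per group and 104 in total.

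This reproduces section 8.1. It concerns the primary outcome and is not in question. The check below takes the SD from it, and uses the 30% allowance as an upper bound on planned loss while ill, because that figure combines withdrawal with missing data.

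**Assumptions not in the protocol.** True time to last watery stool is gamma-distributed with mean 3 or 4 days. Patients are lost at a time uniform between 12 and 48 hours while still ill. The recorded value is the time of loss, which is slightly generous, since the last watery stool may be earlier. Loss rates by arm are chosen for illustration.

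**Formula.** The mean of an arm with proportion w lost while ill falls by about

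w × (mean true duration of those lost − mean recorded duration).

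The mean recorded duration of those lost is (12 + 48) / 2 = 30 h.

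**No true effect, 15% against 5% lost (difference 0.10).**

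- Loss unrelated to eventual duration: 0.10 × (72 − 30) = 4.2 h for a mean of 3 days, and 0.10 × (96 − 30) = 6.6 h for 4 days. Simulation, which also conditions on being ill at the time of loss, gives 4.6 to 6.7 h.
- Loss from the slower half only: the mean of the upper half is about 0.80 SD above the overall mean (normal approximation), or 1.04 days. That is 4.04 days (97 h) and 5.04 days (121 h). Then 0.10 × (97 − 30) = 6.7 h and 0.10 × (121 − 30) = 9.1 h. Simulation gives 6.6 to 9.0 h.
- At 52 per arm, the false-positive rate of the t-test across these cases is about 12% to 26%, against a nominal 5%.

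**No true effect, 15% against 10% lost (difference 0.05).** The same sums halve: 2.1 to 3.3 h when loss is unrelated to duration, and 3.4 to 4.6 h from the slower half. Simulation agrees, at about 2 to 4.5 h overall.

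**True 24 h benefit, 15% lost in each arm.** If those lost have the same recorded mean in both arms, the difference kept is (1 − 0.15) × 24 = 20.4 h. Simulation gives 20.3 to 22.0 h.

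**A heavier case.** Suppose instead that loss is spread over the whole illness and control means are 3 to 5 days. Then 30% against 10% lost gives a false difference of 0.35 to 0.55 day (8.4 to 13.2 h) and a type I error of about 24% to 38%.

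**Patients still ill at the end of the diary.** Under the gamma assumption only 0.8% (mean 3 days) to 2.3% (mean 4 days) exceed 7 days. Truncation at Day 7 is therefore a small part of the problem.

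**The case against.** The strongest reply is that the protocol contains no rule scoring a withdrawn patient as recovered. Section 4.4 only permits earlier data to be used, section 8.2 leaves missing-data methods open, and a SAP that is not shown may add censoring. That stands as a limit on wording: a reader might infer that the protocol declares such patients recovered, and it does not. It does not remove the point. The definition and the named tests are fixed in the protocol and together yield a usable number, so a missing-data rule need not be triggered. A SAP that added censoring would be correcting the protocol's definition, not filling in a detail.

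A reader might also infer that these patients would go unnoticed. The documents do not support that. Section 8.2 requires a CONSORT flow diagram and reporting of missing data. The per-protocol population (section 8.3.2) requires completion of Days 0 to 7, and section 9.3 treats a diary missing for a whole day as an example of a violation. A patient with no soft or firm stool is visibly missing on the primary outcome. The patient can be seen; only the derived ITT value for this outcome looks complete. The per-protocol set still keeps completers who are ill at the end of Day 7, but they are few.

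The loss rates are indeed assumed, and a 15% against 10% split halves the effect. The 24-hour yardstick is the primary outcome's target, not one set for this outcome. Nor does the protocol assign this outcome the task of checking for relapse after a first soft stool, so it cannot be faulted for failing at that.

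Finally, censoring alone is not a full cure. When the sicker patients withdraw, Kaplan-Meier estimates still leave a false advantage of about 2.5 to 3.0 h in the 7-day restricted mean at 15% against 5% loss. That stands and shapes the fix.

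**Conclusion.** The point holds for the ITT analysis of one secondary outcome. As defined, the outcome can turn loss while ill into a short duration. At 15% against 5% lost while ill and no true effect, the false advantage is about 4 to 9 hours; at 15% against 10% it is about 2 to 4.5 hours; with equal 15% loss, a true 24-hour difference is recorded as about 20 to 22 hours. Only the SD comes from the protocol. The means, distribution, timing and split of losses are assumptions, so these figures illustrate size and predict nothing about this trial.

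The direction depends on which arm loses more sick patients. It would be wrong to read this as a bias towards Enterosgel: equal loss works against a true benefit. It would also be wrong to carry the problem over to the primary outcome or the sample size, which do not depend on this definition. It should be corrected, but it does not threaten the trial's main conclusion.

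**What to change.** Replace item 1 in section 3.2.2 with a definition along these lines: time from randomisation to the last watery stool, counted as the end of diarrhoea only if (a) it is followed by a soft or firm stool, or by a pre-specified watery-free interval, and (b) the diary continues through a pre-specified observation period, or to end of Day 7, with no further watery stool. Both conditions are needed. Without (b), a soft stool just before withdrawal would again pass as recovery. The lengths of the interval and the observation period should be set and justified as outcome criteria before the data are seen.

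In section 8.2, censor patients who do not meet this definition at their last diary entry, and compare arms on this outcome by Kaplan-Meier and log-rank. Because withdrawal for deterioration makes that censoring informative, add a sensitivity analysis that scores patients withdrawn while ill as unresolved to end of Day 7.

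The cost is one definition and a few lines of analysis text. The diary in Appendix C already records the time and consistency of every stool, so no new data are needed. Some durations become censored, and precision on this outcome falls slightly.
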